### **1.2.2. Rationale of Disease Selection for Phase 1 Study**

NC525 has been extensively studied in AML and shows promising pre-clinical results, notably targeting LSCs while sparing HSCs. Therefore, it is naturally appropriate to start the FIH dosing in AML.

NC525 has no effects on solid tumors based on pre-clinical models. Therefore, it is not feasible to do a FIH dose escalation study in solid tumors to define a recommended dose for AML. In addition, relapsed refractory Chronic myelomonocytic leukemia (CMML) and MDS were chosen for FIH dosing since CMML and MDS are relatively slowly progressing myeloid malignancies.

### **1.2.3. Rationale for Efficacy Endpoints**

The goal of AML treatment is to control and, ideally, to eradicate disease. Being a Phase 1 study, the primary endpoint is safety and tolerability. Because of its sparing effect on normal HSCs, the aim is also to decrease the incidence of cytopenia-related complications.

Efficacy will be assessed as a secondary endpoint and will include Objective Response (OR), Event-free survival (EFS), and Overall survival (OS).

Efficacy measures for AML have been well established. The European Leukemia Net (ELN) has recently updated the guidelines on response criteria in AML (See [Section 1.2.3.1 Response Criteria](#)). Ideally, the purpose of an induction therapy is to achieve complete remission (CR). Once the CR is achieved, further therapies are given as consolidation and/or maintenance to deepen the remission and maximize response duration. However, since NC525 has not been tested in humans, despite its potential to eradicate leukemic stem cells from pre-clinical studies, there is understanding that transplant eligible patients will likely undergo allogeneic stem cell transplant at the discretion of the treating investigator. Assessing optimal value of the study drug will come from observing treatment effect of NC525 in patients who are ineligible for allogeneic stem cell transplant (SCT).

#### **1.2.3.1. Response Criteria for Disease Assessment**

Disease Assessments will be performed using the European Leukemia Net (ELN) Guidelines ([Döhner et al. 2022](#)) as outlined in the Schedule of Study Procedures ([Table 7](#)) and [Appendix 6](#) for the ELN Outcome Measures.

Criteria for Efficacy Measures evaluation are as follows ([Döhner et al. 2022](#)):

- Complete Remission (CR): Absolute neutrophil count  $> 1,000/\mu\text{L}$ , platelets  $\geq 100,000/\mu\text{L}$ , red cell transfusion independence, and bone marrow with  $< 5\%$  blasts.
- CR with partial hematologic recovery (CRh): Absolute neutrophil count  $> 500/\mu\text{L}$ , platelets  $\geq 50,000/\mu\text{L}$ , otherwise all other CR criteria are met.
- Complete Remission with Incomplete Blood Count Recovery (Cri): Bone marrow with less than 5% blasts, and absolute neutrophils of  $< 1,000/\mu\text{L}$  or platelets  $< 100,000/\mu\text{L}$ .
- Partial Remission (PR): All of the hematologic values for a CR but with a decrease of at least 50% in the percentage of blasts to 5% to 25% in the bone marrow aspirate.
- Morphologic Leukemia-free State (MLFS): Less than 5% blasts in an aspirate sample with marrow spicules and with a count of at least 200 nucleated cells, absence of blasts with Auer rods, absence of circulating blasts, absence of extramedullary disease, no hematologic recovery required.
- No Response: Patients evaluable for response but not meeting the criteria for CR, CRh, CRi, MLFS or PR are categorized as having no response prior to the response landmark. Patients failing to achieve response by the designated landmark are designated as having refractory disease.
- Non-evaluable Response: Non-evaluable for response will include patients lacking an adequate bone marrow response evaluation. This category will include patients with early death, withdrawal prior to response assessment, or a technically suboptimal bone marrow sample precluding assessment

Response should be based on the most recent bone marrow and hematology panel values. For subjects who require a delay in study treatment for peripheral blood count recovery after a bone marrow evaluation, hematology panel values for 2 weeks from the bone marrow analysis can be used to determine the ELN response. As a significant number of the subjects in this study may have antecedent hematologic illnesses, hematologic response will also be evaluated.

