### **2.2.2. Secondary Endpoints**

- 1) Assessment of anti-leukemia activity/efficacy will be used to evaluate the clinical benefit of NC525, including:
  - a. Objective Response (OR)
    - CR, CRi, or CRh and MLFS
  - b. Event-free survival (EFS), and
  - c. Overall survival (OS)
- 2) Assessment of time to achieve response, defined as CR, CRi, or CRh

- a. To evaluate the time to achieve an objective response from Cycle 1 Day 1 to day remission is achieved as defined per protocol
- 3) Assessment of PK of NC525 concentration(s) in serum, as well as assessment of the PK/PD profile

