**Figure 1: Phase 1 Study Design**

[figure not shown]
The safety and tolerability of NC525 will be evaluated by escalating dose levels of NC525. In addition, the minimally active dose (MAD), pharmacologically active dose (PAD), and maximum tolerated dose (MTD), of NC525 will be determined.

The PAD will be defined as a dose that provides a maximal biologic effect, such as achieving a complete remission (CR) and other variants of complete remission (CRh, CRi), and/or the MTD of NC525.

Once the biologically-effective dose(s) deemed to be safe have been identified, the safety and tolerability will be further assessed through expansion of two dose levels to determine an optimal Recommended Phase 2 Dose (RP2D) and administration schedule of NC525.

A Bayesian Optimal Interval (BOIN) design (Figure 2) with conventional 3+3 escalation rule fully nested for Phase I clinical trials (Liu S, Yuan Y, 2015) with a target dose-limiting toxicity (DLT) rate of approximately 25% will be applied for dose escalation and confirmation to determine a recommended Phase 2 dose (RP2D) for NC525.

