### 4.1. Subject Inclusion Criteria

**Subjects are eligible to be included in the study only if all of the following criteria apply:**

- 1) The subject is willing to provide written informed consent for the trial.
- 2) Be  $\geq$  18 years of age on the day of signing informed consent.
- 3) Subject has one of the following Myeloid Neoplasms determined by pathology review at the treating institution:

- Relapsed or Refractory AML,

**Note:** Active, relapsed, or refractory AML is defined as any one of the following:

- Primary induction failure, or (PIF) after 2 or more cycles of therapy,
- First early relapse after a remission duration of fewer than 6 months,
- Relapse refractory to salvage combination chemotherapy second or subsequent relapse, or
- Relapsed or refractory AML with at least 5% blasts by bone marrow biopsy or aspirate, or at least 1% blasts in peripheral blood

- Relapsed or Refractory Myelodysplastic syndrome (MDS) after prior hypomethylating agents

**Note:** Subject must have sub-type MDS-EB2 with 10-19% blasts by bone marrow biopsy or aspirate.

- Relapsed or Refractory Chronic myelomonocytic leukemia (CMML) with progressive disease or lack of response to hypomethylating agents

- 4) A male subject must agree to use approved contraception (based on institutional guidelines) and refrain from sperm donation or expecting to father a child, from Screening through the treatment period and for at least 90 days after the last dose of study treatment.

- 5) A female subject is eligible to participate if she is not pregnant, not breastfeeding, and at least one of the following conditions applies:

- a) Not a woman of childbearing potential (WOCBP)
- b) A WOCBP agrees to follow approved contraceptive guidance (based on institutional guidelines) from Screening through the treatment period and for at least 90 days after the last dose of study treatment.

- 6) Have an Eastern Cooperative Oncology Group (ECOG) performance status of 0 to 2.
- 7) Life expectancy greater than or equal to 12 weeks as judged by the Investigator.
- 8) Have adequate organ function as defined in the following table ([Table 3](#))

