## APPENDIX 6: OUTCOME MEASURES (EUROPEAN LEUKEMIA NET (ELN) 2022, BLOOD JULY 2022 (ONLINE VERSION)

### Outcome measures for clinical trials in acute myeloid leukemia

Category	Definition
Early death	Death from any cause within a timeframe relevant for the therapy being investigated (e.g., 30 and 60 days from commencing therapy)
Overall survival	Defined for all patients in a trial; measured from day 1 of randomization or day 1 of registration in non-randomized trials (or from the date of diagnosis, e.g., for correlative science studies) to the date of death from any cause; patients not known to have died at last follow-up are censored on the date they were last known to be alive
Event-free survival (EFS)	Defined for all patients in a trial; measured from day 1 of randomization or day 1 of registration in non-randomized trials to the date of treatment failure, hematologic relapse from CR/CRh/CRi or death from any cause, whichever occurs first; treatment failure is defined as not achieving either CR, CRh or CRi by a pre-defined landmark (e.g., after two cycles of intensive chemotherapy or 180 days for non-intensive therapy); patients evaluable for response but not achieving either CR, CRh or CRi by the defined landmark and patients who die before the defined landmark without response assessments are considered an event at day 1 of randomization; patients alive who are non-evaluable for response should be censored at day 1 of the randomization; patients achieving either CR, CRh or CRi by the defined landmark but do not relapse or die should be censored on the date they were last assessed for response
Relapse-free survival (RFS)a	Defined only for patients achieving complete remission CR, CRh, or CRi; measured from the date of achievement of remission until the date of hematologic relapse or death from any cause; patients not known to have relapsed or died at last follow-up are censored on the date they were last known to be alive
Cumulative incidence of relapse (CIR)	Defined for all patients achieving CR, CRh, CRi; measured from the date of achievement of a remission until the date of hematologic relapse; patients not known to have relapsed are censored on the date they were last assessed for response; patients who died without relapse are counted as a competing cause of failure

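### The written CR, CRh and CRi criteria omit the leukemia-clearance conditions that MLFS carries, so a subject with persisting blood blasts can be classed as a remission

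*Combined protocol and SAP*

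**What the plan says.** Section 1.2.3.1 cites the ELN guideline and then writes out the criteria.

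- **CR:** neutrophils above 1,000/µL, platelets at least 100,000/µL, "red cell transfusion independence, and bone marrow with" fewer than 5% blasts.
- **CRh:** neutrophils above 500/µL, platelets at least 50,000/µL, and "otherwise all other CR criteria are met".
- **CRi:** "Bone marrow with less than 5% blasts, and absolute neutrophils of" below 1,000/µL, or platelets below 100,000/µL. There is no lower limit on counts and no clause carrying over the other CR criteria.
- **MLFS:** marrow blasts below 5% in an adequate aspirate, with "absence of blasts with Auer rods, absence of circulating blasts, absence of extramedullary disease, no hematologic recovery required".

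The endpoints use these categories differently. Objective response in Section 2.2.2 counts CR, CRi, CRh and MLFS. The next endpoint leaves MLFS out: "Assessment of time to achieve response, defined as CR, CRi, or CRh". So does EFS in Appendix 6, where "treatment failure is defined as not achieving either CR, CRh or CRi by a pre-defined landmark". Section 10.2.2 stops for futility at 2 or fewer responses in 14 and calls the treatment promising at 9 or more in 28, without defining a response. In Section 4.1, the fourth of the four AML entry alternatives accepts relapsed or refractory disease with at least 5% marrow blasts "or at least 1% blasts in peripheral blood".

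**The concern.** MLFS is the lowest category in objective response, yet it is the only one that requires the blood to be clear of blasts. A subject whose marrow has fallen below 5% but who still has leukemic cells in the blood is denied MLFS and given a higher label. That label starts the time-to-response clock, counts as remission for EFS and adds a responder. In an open-label study with several sites, the classification would then depend on whether an investigator applies a condition that is not written down.

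A second, separate problem is that CRi has no count floor and MLFS needs no count recovery. The two definitions therefore describe largely the same subjects, although the plan treats them differently for time to response and EFS.

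**Working it through.** **1. The blast conditions side by side (Section 1.2.3.1)**

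| Condition | CR | CRh | CRi | MLFS |
|---|---|---|---|---|
| Marrow blasts <5% | yes | yes | yes | yes |
| No circulating blasts | – | – | – | yes |
| No Auer rods | – | – | – | yes |
| No extramedullary disease | – | – | – | yes |
| Neutrophils (/µL) | >1,000 | >500 | <1,000, or the platelet limit | none |
| Platelets (/µL) | ≥100,000 | ≥50,000 | <100,000, or the neutrophil limit | none |
| Red cell transfusion independence | yes | yes | – | – |

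**2. Worked subjects**

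- Marrow 4%, blood blasts 3%, neutrophils 600: fails MLFS (circulating blasts) and meets CRi (marrow <5%, neutrophils <1,000). If platelets are at least 50,000 and no red cells are transfused, CRh is met as well.
- Marrow 3%, blood blasts 2%, neutrophils 1,500, platelets 150,000, transfusion independent: fails MLFS and meets CR.
- An AML subject who enters on blood blasts alone, with marrow below 5% and cytopenia, already meets the CRi wording at screening.

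**3. Overlap of CRi with MLFS**

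Take subjects who meet every MLFS condition. Cross neutrophils (300, 800, 1,000, 1,500), platelets (30,000, 70,000, 150,000) and red cell independence (yes, no): 4 × 3 × 2 = 24 profiles.

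- CRi: neutrophils 300 or 800 give 2 × 3 × 2 = 12. Neutrophils 1,000 or 1,500 with platelets 30,000 or 70,000 give 2 × 2 × 2 = 8. Total 20 of 24.
- CR or CRh: 6 of 24, of which 4 are also CRi. At least one of CR, CRh, CRi: 20 + 6 − 4 = 22 of 24.
- Not CR or CRh: 24 − 6 = 18. Of these, 20 − 4 = 16 are CRi.
- MLFS only: 18 − 16 = 2. Both have neutrophils of at least 1,000 and platelets of at least 100,000 but still need red cell transfusions.

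A neutrophil count of exactly 1,000 does not by itself leave a subject in MLFS: with platelets of 150,000 and transfusion independence it is CRh. These counts show logical overlap. They are not patient frequencies.

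**4. The response rule**

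The plan's figures come first. With 14 subjects per stage and response rate p:

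- early stopping = P(X₁ ≤ 2), X₁ ~ Bin(14, p)
- claim promising = Σ over x₁ ≥ 3 of P(X₁ = x₁) × P(X₂ ≥ 9 − x₁), X₂ ~ Bin(14, p)
- average size = 14 + 14 × (1 − early stopping)

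At p = 0.2, early stopping = 0.8¹⁴ + 14(0.2)(0.8¹³) + 91(0.04)(0.8¹²) = 0.0440 + 0.1539 + 0.2501 = 0.4481. Average size = 14 + 14 × 0.5519 = 21.73. Claim promising = 8.67%. Table 15 gives 44.81%, 21.7 and 8.67%. Its rows for 0.4 and 0.5 reproduce too.

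Next, a sensitivity calculation. **The added share is assumed, because the documents give none.** It also assumes that 'response' means objective response. The true rate is 0.20, and the share is subjects counted as CR, CRh or CRi despite circulating blasts.

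| Assumed added share | Expected such subjects in 28 | Early stopping | Claim promising |
|---|---|---|---|
| 0 | 0 | 44.81% | 8.67% |
| 2.5 points | 0.7 | 35.91% | 15.36% |
| 5 points | 1.4 | 28.11% | 24.21% |
| 10 points | 2.8 | 16.08% | 46.06% |
| 15 points | 4.2 | 8.39% | 67.80% |

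**The case against.** **The ELN guideline is cited.** Section 1.2.3.1 says assessments follow it, so the bullets may be an abbreviation. That is possible. But the section presents the list as the criteria for evaluation, Appendix 6 reproduces only outcome measures, and nothing says which source prevails. The citation is a reason to reconcile the two, not a cure.

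**Other safeguards exist.** Response uses the hematology panel, which records blasts if detected (Table 8). Subjects with extramedullary disease are named in exclusion criterion 3. Blast clearance is named in Section 3.2.1, and marrow goes for retrospective central response analysis. These show that the data exist and that extramedullary disease should be uncommon at entry. None makes blood clearance a condition of CR, CRh or CRi; Section 3.2.1 treats it as a pharmacodynamic marker. On specimen quality the objection largely stands: a technically suboptimal marrow is non-evaluable in every category, and Section 8.9.2 requires a sufficient aspirate and core.

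**Efficacy is secondary and the rules are permissive.** This is true, and it limits the consequence. The categories still need to mean what the endpoints take them to mean.

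A reader might infer more than the documents support:

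- *That CR and CRh are looser than MLFS overall.* They are stricter on counts and transfusion; they lack only the clearance items.
- *That the CRi/MLFS overlap inflates objective response.* It cannot, because both count. Only subjects who fail MLFS add responders.
- *That MLFS is barred from the pharmacologically active dose.* Section 3.1 offers remission categories as examples ("such as achieving a complete remission (CR) and other variants of complete remission (CRh, CRi") and adds the MTD as an alternative.
- *That subjects with blood blasts generally still meet the entry definition.* The 1% threshold is in one of four AML alternatives, and AML is one of three eligible diseases.
- *That CRi needs a one-lineage rule or a transfusion-support condition on counts.* Nothing in the documents calls for either.

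**Conclusion.** The point holds for the clearance conditions. As written, a subject with marrow blasts below 5% and persisting circulating blasts is CRi if cytopenic, or CR or CRh if counts and transfusion status allow, while failing MLFS. That subject is a responder for objective response, time to response and EFS. The effect on the 3-of-14 and 9-of-28 counts is conditional on 'response' in Section 10.2.2 meaning objective response.

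The overlap of CRi with MLFS is a second and smaller defect, confined to time to response and EFS.

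The size is unknown. The sensitivity table shows that a few such subjects among 28 would matter; it does not show that they will occur. The conclusion rests on the written list being the one applied. If the cited guideline is meant to govern, the text must say so and the list must agree with it.

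**What to change.** 1. In Section 1.2.3.1, add to CR, CRh and CRi the clearance conditions already stated for MLFS: no circulating blasts, no Auer rods, no extramedullary disease.
2. Assign each subject the single highest category met, in the order CR > CRh > CRi > MLFS > PR.
3. State whether the written list or the cited ELN guideline governs, and make them agree.
4. Reconcile CRi and MLFS so that they are distinguishable. Steps 1 and 2 alone do not achieve this: 20 of the 24 MLFS profiles would still meet CRi. Where the boundary lies is for the sponsor to decide and write down.
5. Define 'response' in Section 10.2.2.

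The cost is protocol wording and a programmed derivation. Blood differentials with blasts and marrow assessments are already collected (Tables 8 and 10). The change should be made before responses are classified, so that it is not driven by the data. Reported CR/CRh/CRi and objective response rates may be slightly lower. Reaching CR, CRh or CRi also permits the switch from weekly to biweekly dosing (Sections 3.2.2 and 7.3), so those sections must be reconciled with the revised definitions.

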### **1.3. Research Hypotheses**

Treatment with NC525, a humanized immunoglobulin gamma 1, kappa (IgG1κ) monoclonal antibody specific for LAIR-1, will, specifically kill leukemic cells while sparing healthy cells in both the bone-marrow and the periphery, ameliorating disease with minimal toxicity, and resulting in clinical benefit for subjects with advanced myeloid neoplasms.

## **2. STUDY OBJECTIVES AND ENDPOINTS**

### **2.1. STUDY OBJECTIVES**

#### **2.1.1. Primary Objectives**

- 1) To evaluate the safety, tolerability, and dose-limiting toxicities (DLTs) of NC525
- 2) The recommended Phase 2 dose (RP2D) of NC525 will be defined in subjects with advanced myeloid neoplasms
- 3) Define a minimally active dose (MAD), pharmacologically active dose (PAD), and maximum tolerated dose (MTD) of NC525 in subjects with advanced myeloid neoplasms

#### **2.1.2. Secondary Objectives**

- 1) To evaluate the clinical benefit of NC525
- 2) To evaluate the time to achieve an objective response (OR)
- 3) To evaluate the pharmacokinetic (PK) and pharmacodynamic (PD) profiles of NC525

#### **2.1.3. Exploratory Objectives**

- 1) To assess the immunogenicity of NC525
- 2) To explore biomarkers that may predict the pharmacologic activity of NC525

## **2.2. STUDY ENDPOINTS**

### **2.2.1. Primary Endpoints**

- 1) Safety and tolerability will be assessed by monitoring the frequency, duration, and severity of adverse events (AEs). **Note:** Toxicity grading per NCI CTCAE v5.0
- 2) The recommended Phase 2 dose (RP2D) of NC525 in subjects with advanced myeloid neoplasms.
- 3) The MAD, PAD, and MTD of NC525 will be defined in subjects with advanced myeloid neoplasms.

### **2.2.2. Secondary Endpoints**

- 1) Assessment of anti-leukemia activity/efficacy will be used to evaluate the clinical benefit of NC525, including:
  - a. Objective Response (OR)
    - CR, CRi, or CRh and MLFS
  - b. Event-free survival (EFS), and
  - c. Overall survival (OS)
- 2) Assessment of time to achieve response, defined as CR, CRi, or CRh

- a. To evaluate the time to achieve an objective response from Cycle 1 Day 1 to day remission is achieved as defined per protocol
- 3) Assessment of PK of NC525 concentration(s) in serum, as well as assessment of the PK/PD profile

### **2.2.3. Exploratory Endpoints**

[figure not shown]
- 1) Immunogenicity, defined as the occurrence of anti-drug antibodies (ADA) to NC525, will be determined
- 2) Biomarker effects of NC525 in peripheral blood and bone marrow will be assessed, including but not limited to the following:
  - a. Percentage and/or expression level of LAIR-1 blast cells and/or Leukemic Stem Cells (LSC) or Hematopoietic Stem Cells (HSC)
  - b. Any relation to response (clearing of blast cells to achieving CR)
  - c. Serum markers of inflammation or immune modulation (cytokine & chemokine levels)

### 3. STUDY DESIGN

#### 3.1. Description of the Study

This is an open-label, non-randomized, Phase 1 study to determine the safety and tolerability of NC525. This study will also assess the clinical benefit in subjects with advanced myeloid neoplasms. The study includes a dose escalation phase to determine MTD followed by expansion cohorts to further evaluate the safety and tolerability of the MTD (Figure 1).

**Figure 1: Phase 1 Study Design**

[figure not shown]
The safety and tolerability of NC525 will be evaluated by escalating dose levels of NC525. In addition, the minimally active dose (MAD), pharmacologically active dose (PAD), and maximum tolerated dose (MTD), of NC525 will be determined.

The PAD will be defined as a dose that provides a maximal biologic effect, such as achieving a complete remission (CR) and other variants of complete remission (CRh, CRi), and/or the MTD of NC525.

Once the biologically-effective dose(s) deemed to be safe have been identified, the safety and tolerability will be further assessed through expansion of two dose levels to determine an optimal Recommended Phase 2 Dose (RP2D) and administration schedule of NC525.

A Bayesian Optimal Interval (BOIN) design (Figure 2) with conventional 3+3 escalation rule fully nested for Phase I clinical trials (Liu S, Yuan Y, 2015) with a target dose-limiting toxicity (DLT) rate of approximately 25% will be applied for dose escalation and confirmation to determine a recommended Phase 2 dose (RP2D) for NC525.

